6. TREATMENT OF SUBJECTS

All vaccines associated with this study are to be stored separately from other vaccines and medications in a secure location under appropriate storage conditions with temperature monitoring. **All vaccines associated with this study must be checked for expiration date prior to use. Expired vaccines must not be administered to subjects.**

6.1 Study Vaccine(s)

The term ‘study vaccine’ refers to those vaccines provided by the Sponsor or delegate, which will be evaluated as part of the study objectives. The study vaccines specific to this study are described below.

Investigational Vaccine: QIVc

An approximately 0.5 mL dose of QIVc (cell-derived seasonal quadrivalent influenza vaccine) contains nominally 15 µg of hemagglutinin (HA) of each of the 2 influenza type A strains and each of the 2 influenza type B strains for a total of 60 µg of HA in the vaccine. The strain composition will be that recommended by the WHO for quadrivalent influenza vaccines contemporaneous to the timing of the study. The full composition of the vaccine is reported in [Table 6.1-1](#).

Table 6.1-1: QIVc Vaccine Composition

Names of Ingredients	Quantity per dose* (0.5 mL/dose)	Function
Active Ingredients Haemagglutinin (HA) and Neuraminidase (NA) antigens from the influenza virus strains recommended by the WHO / CBER/ CHMP for the respective season Strain A1 Strain A2 Strain B1 Strain B2	≥ 15µg HA (per strain)	Influenza Vaccine
Other Ingredients		
Buffer M (PBS) pH 7.2		
sodium chloride	4.0mg	Isotonic aid
potassium chloride	0.1mg	Isotonic acid
magnesium chloride hexahydrate	0.05mg	Stabilizer
disodium hydrogen phosphate dihydrate	0.646mg	Buffer

Names of Ingredients	Quantity per dose* (0.5 mL/dose)	Function
potassium dihydrogen phosphate	0.1865mg	Buffer
Water for injection	Up to 0.5 mL	diluent

* the quantities indicated in this table reflect the amount in a 0.5 mL dose.

** residues of special relevance: beta-propiolactone, cetyltrimethylammonium bromide and polysorbate 80.

Non-influenza comparator vaccine:

Meningococcal (Group ACWY) Conjugate Vaccine

Menveo® will be used as non-influenza comparator vaccine.

Menveo® is a meningococcal (Groups A, C, Y and W-135) oligosaccharide diphtheria CRM197 conjugate vaccine for intramuscular injection. Menveo is supplied in two vials that must be combined prior to administration, to reconstitute the MenA lyophilized conjugate vaccine component with the MenCYW-135 liquid conjugate vaccine component immediately before administration.

For a comprehensive review of Menveo® please refer to the Summary of Products Characteristics/ Package Insert supplied by Seqirus or delegate; this document should be reviewed by the Investigators prior to initiating the study.

Saline Placebo

The saline placebo is a clear, colorless liquid. The dose to be administered is 0.5 mL and has the following composition per dose (0.5 mL):

Table 6.1-2 Composition of Saline Placebo

Component	Unit and/or Percentage Formula (Dose 0.5 mL)
Sodium chloride	4.5 mg
Water for injection	Qs to 0.5 mL

6.2 Non-Study Vaccines

The term ‘non-study vaccine’ refers to those vaccines which will be intentionally given to study subjects but not formally included in the analysis of study objectives. Non-study vaccines will not be provided by Seqirus.

6.3 Vaccine Preparation and Administration

The vaccine must be prepared according to the instruction sheet (QIVc) or package insert Menveo® before use. Expired vaccines must not be administered.

The investigator or designee will be responsible for oversight of the administration of vaccine to subjects enrolled in the study according to the procedures stipulated in this study protocol. All vaccines will be administered only by unblinded personnel who are qualified to perform that function under applicable local laws and regulations for the specific study site.

QIVc will be provided in prefilled syringes (PFS), with an injectable volume of approximately 0.5 mL. The full volume contained in the PFS is to be administered. Menveo is supplied in two vials that must be combined prior to administration, to reconstitute the MenA lyophilized conjugate vaccine component with the MenCYW-135 liquid conjugate vaccine component immediately before administration.

Vaccination will be performed intramuscularly, preferably in the deltoid muscle of the non-dominant arm.

Detailed vaccine preparation and administration instructions will be provided to investigators in the Protocol Ancillary Document prior to study start.

PRECAUTIONS TO BE OBSERVED IN ADMINISTERING STUDY VACCINE:

Prior to vaccination, subjects must be determined to be eligible for study vaccination and it must be clinically appropriate in the judgment of the investigator to vaccinate. Eligibility for study vaccine administration is determined by evaluating the entry criteria outlined in protocol [Sections 4.1, Inclusion Criteria](#) and [4.2, Exclusion Criteria](#).

Delay of study vaccination is determined by following the criteria outlined in [Section 4.3, Criteria for Delay of Vaccination](#).

Study vaccines should not be administered to individuals with known hypersensitivity to any component of the vaccines.

Shake the vaccine well before use to form a homogeneous suspension. The vaccine should be visually inspected for particulate matter and discoloration prior to administration. In the event of any foreign particulate matter and/or variation of physical aspect being observed, do not administer the vaccine and contact the Sponsor and report the issue as a Pharmaceutical Technical Complaint. Do not discard the vaccine until authorized by Seqirus.

Standard vaccination practices are to be observed and care should be taken to administer the injection intramuscularly. Before administering vaccine, the vaccination site is to be disinfected with a skin disinfectant (e.g., 70% alcohol). Allow the skin to dry. **DO NOT inject intravascularly.**

As with all injectable vaccines, trained medical personnel and appropriate medical treatment should be readily available in case of anaphylactic reactions following vaccine administration. For example, epinephrine 1:1000, diphenhydramine, and/or other medications for treating anaphylaxis should be available.

6.4 Vaccine Administration Error or Overdose of Vaccine

Vaccine administration error is defined as receiving a dose of study vaccine that was not reconstituted as instructed or administered by a different route from the intended route of administration. An overdose of study vaccine (whether accidental or intentional) is defined when a dosage higher than the recommended dosage (as per the QIVc dosing regimen referred to in [Table 6.1-1](#) or as per the package insert of Menveo®) is administered.

Any vaccine administration error or overdose of study vaccine detailed in this protocol must be reported as an adverse event, and if the vaccine administration error or overdose is associated with a SAE, it must be reported as such within 24 hours to the Sponsor.

6.5 Prior and Concomitant Medications and Vaccines

Data on medications including any vaccinations that were taken by the subject up to 2 months prior to enrollment will be recorded in the source documents and collected on the relevant Prior and Concomitant Medications eCRF. Data on influenza vaccinations that were administered to the subject up to 6 months prior to enrollment will be recorded in the source documents and collected on the Prior and Concomitant Medications eCRF.

When recording prior and concomitant medications/vaccinations, these should be checked against the study entry and continuation criteria in [Sections 4.1](#) through [4.3](#) to ensure that the subject should be enrolled/continued in the study.

The use of antipyretics and/or analgesic medications within 24 hours prior to vaccination must be identified and the reason for their use (prophylaxis versus treatment) must be described in the source documents and/or diary card and Concomitant Medications eCRF.

Medications taken for prophylaxis are those intended to prevent the onset of symptoms. Medications taken for treatment are intended to reduce or eliminate the presence of symptoms that are present.

From study entry through termination, concomitant medications will be recorded in the Concomitant Medications eCRF as outlined below:

- All medications, with the exception of vitamins and minerals, will be recorded beginning from the time of vaccination and continuing for 21 days following each vaccination received.
- Medications associated with SAEs, AEs leading to study withdrawal, NOCDs, and all vaccinations will be recorded from Day 1 to Day 181, or until the end of influenza season whichever is longer, for “previously vaccinated” subjects and from Day 1 to Day 209, or until the end of influenza season whichever is longer, for “not previously vaccinated” subjects.
- All medications associated with any medically-attended adverse events within 30 days after the ILI onset

The following treatments, if used within the Treatment Period (Day 1 through 3 weeks following subject’s last study vaccination only), e.g., in case of a medical need, represent a protocol deviation and may result in the subject being excluded from the Per Protocol Set (PPS):

- Cancer chemotherapy.
- Immunosuppressive agents or systemic corticosteroids at any dose (topical, inhaled, and intranasal corticosteroids are permitted). A single dose of intra-articular corticosteroids is also permitted).
- Blood, blood products and/or plasma derivatives or any parenteral immunoglobulin preparation.
-
- Any non-study investigative agents.

A non-study influenza vaccination(s) is considered a protocol deviation if received from Day 1 until the end of season or Day 181/ 209 whichever comes first and may result in the subject being excluded from the Per Protocol Set (PPS).

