sBLA	Supplement Biologics License Application
SC	Seroconversion
SDA	Source Data Agreement
SH	Southern Hemisphere
SOC	System Organ Class
SOP	Standard Operating Procedure
TIV	Trivalent Influenza Vaccine
VRBPAC	Vaccines and Related Biological Products Advisory Committee
VSAE	Vaccine Serious Adverse Events
WHO	World Health Organization

DEFINITIONS

End of influenza season: The end of the influenza season will be defined as the end of June for Northern Hemisphere (NH) influenza seasons and end of December for Southern Hemisphere (SH) influenza seasons. For tropical countries, with no typical NH or SH influenza season, the season is defined by the use of the strains in the vaccine formulation (i.e. strains as recommended for the NH or the SH influenza season) and the timing of vaccination.

End of study: Evaluation of the primary and secondary efficacy objectives requires the testing of biological samples from the study subjects, which can only be completed after all samples are collected. Nasopharyngeal swabs may be collected up to end of influenza season. For the purpose of this protocol, end of study is defined as the completion of the testing of such biological samples, to be achieved no later than 8 months after LSLV.

Influenza case: An ILI associated with RT-PCR or culture confirmed influenza.

Influenza-like illness (ILI) onset: The first day on which a subject fulfils the criteria for protocol-defined ILI.

Medically-attended Adverse Event: Defined as symptoms or illnesses requiring hospitalization, or emergency room visit, or visit to/by a health care provider.

Study definition of Influenza-like illness (ILI): Fever of $\geq 37.8^{\circ}\text{C}$ (100°F) and at least one of the following: cough, sore throat, nasal congestion, or rhinorrhea.

Qualified healthcare professional: Any licensed health care professional who is permitted by institutional policy to perform clinical interventions and assessments such as physical examinations and who is identified within the Study Staff Signature Log.

Trained healthcare professional: Any health care professional who is permitted by institutional policy and trained to perform delegated tasks and who is identified within the Study Staff Signature Log.

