3.2 Study Period

Each subject should expect to participate in the study for 180 days after last vaccination, or until the end of the influenza season, whichever is longer (i.e. from the time of enrolment through the last study visit).

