8.1.1.2 Primary Efficacy Endpoint(s)

The primary efficacy endpoint is the time from the last study vaccination to the onset of the first occurrence confirmed influenza by either RT-PCR-confirmed or culture-confirmed, due to any influenza Type A or B strain regardless of antigenic match to the strains selected for the seasonal vaccine, occurring >14 days after the last vaccination and until the end of the influenza season.

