11. EFFICACY ANALYSIS

11.1 Primary Efficacy Objectives Analysis

Efficacy will be evaluated in all subjects in relation to cases occurring >14 days after last vaccination and until the end of study or the end of the influenza season, whichever is longer, using the following null (H_0) and alternative (H_1) hypotheses:

$$H_0: 1 - HR = VE \leq 0.2 \quad \text{versus} \quad H_1: 1 - HR = VE > 0.2,$$

where HR is a hazard ratio of QIVc versus non-influenza comparator and VE is vaccine efficacy. The primary objective will be achieved if the lower limit of the two-sided confidence interval of VE estimate, with at least 95% coverage in a multiple sequential hypothesis testing, exceeds 0.2 in subjects ≥ 2 years to <18 years of age.

The co-primary objective will be achieved if the lower limit of the two-sided confidence interval of VE estimate, with at least 95% coverage in a multiple sequential hypothesis testing, exceeds 0.3 in subjects ≥ 3 years to <18 years of age.

The co-primary objective will only be demonstrated in case of successful demonstration of the primary efficacy objective (i.e. in hierarchical testing procedure, only after demonstration of absolute vaccine efficacy of QIVc in subjects ≥ 2 years to <18 years of age).

In case an interim analysis will be performed the 95% CI will be adjusted accordingly. If an interim analysis is performed and the trial doesn't stop, then all the subsequent analysis will be tested at a reduced alpha level, i.e. what's left from the interim analysis. The confidence interval will be higher than 95% instead of 95% for the final analysis.

(Co-)Primary vaccine efficacy analyses will be based on the Efficacy FAS, and repeated on the Efficacy PPS.

For each of the age groups (≥ 2 to <18 and ≥ 3 to <18 years), the HR² and the related 95% CI of HR, for onset of first RT-PCR or culture confirmed influenza will be estimated by a proportional hazards regression model with treatment effect as a fixed effect and stratifying covariates as random effect:

$h_i(t|X) = h_0(t) \exp(\beta^T X + b^T Z)$, with t denoting time to the influenza, β is the effect of treatment group indicated by X , b is random effect (assumed as a multivariable random gaussian variable with zero mean and diagonal covariance matrix), Z is random effect covariate (reflecting randomization strata, see [Section 8.1](#) for further discussion of the covariates utilized).

² Formula: $VE=1-HR$

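### Protocol 6.5 can close the deviation window for non-study influenza vaccine before efficacy follow-up ends, so the per-protocol repeat may keep comparator children vaccinated late

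*Protocol*

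**What the plan says.** Protocol 6.5 makes a non-study influenza vaccination a deviation from Day 1 "until the end of season or Day 181/ 209 whichever comes first". It adds that exclusion from the PPS is possible, not automatic.

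The related windows run longer:

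- **Efficacy cases.** Protocol 8.1.1.2 counts influenza "occurring >14 days after the last vaccination and until the end of the influenza season", and SAP 2.1.2 agrees. SAP 11.1 goes further and counts cases "until the end of study or the end of the influenza season, whichever is longer".
- **Participation.** Under Protocol 3.2 each subject takes part "for 180 days after last vaccination, or until the end of the influenza season, whichever is longer".
- **Recording.** Protocol 6.5 itself records all vaccinations to the later of Day 181/209 and season end.
- **Season end.** The Protocol definitions fix it as "the end of June for Northern Hemisphere (NH) influenza seasons and end of December for Southern Hemisphere (SH) influenza seasons".

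PPS membership depends on deviations judged exclusionary (Protocol 8.3.5, SAP 7.4). SAP 6.1 lists use of an excluded concomitant medication among major deviations, without an end date for non-study influenza vaccine, and leaves the detail to a deviation specification document. SAP 11.1 censors subjects without ILI and dropouts; it does not censor at receipt of a non-study influenza vaccine. The primary efficacy analysis is on the FAS and is repeated on the PPS (Protocol 8.4.2.2.3). SAP 8.2.3 describes that repeat as a robustness check.

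**The concern.** The deviation window takes the earlier of two dates, while participation and vaccination recording take the later, and efficacy cases count to season end. For a child vaccinated in autumn, Day 181 or Day 209 comes before the end of June. After that day a licensed influenza vaccine is recorded but is not a deviation under 6.5, although the child still contributes time at risk and possibly a case.

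The PPS repeat is meant to show the vaccine contrast in children who followed the plan. A comparator child who has since had an influenza vaccine no longer represents the unvaccinated state. Keeping that child's later follow-up lowers the comparator hazard and pulls the per-protocol VE toward zero. What is at stake is how clean the supportive analysis is, not the primary test.

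**Working it through.** **1. Baseline.** The plan's co-primary figure is 381 events (true VE 50%, lower limit above 30%, two-sided 5%, about 90% power; Protocol 8.5). On the margin-shifted scale HR = 0.50/0.70 = 0.714.

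- Schoenfeld: 4 × (1.960 + 1.282)² / (ln 0.714)² = 372 events, within 3% of 381.
- Freedman: 379 events.
- Schoenfeld power at 381 events: 90.7%.

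The figure reproduces and is not in dispute. It serves only as a yardstick in step 4.

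**2. When the window closes early.** Day k is Day 1 + (k − 1). Day 181 is 181 − 1 = 180 days after the only dose; Day 209 is 209 − 29 = 180 days after the second. Counting back from 30 June, there is a gap for a Day 1 before 1 January (one dose) or 4 December (two doses). Counting back from 31 December in the Southern Hemisphere, the dates are 4 July and 6 June. For later starts the window ends at season end and matches Protocol 8.1.1.2, though it is still shorter than SAP 11.1 wherever end of study is later than season end.

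**3. Length of the gap.** The documents give no enrolment dates, so the Day 1 values are assumptions. Protocol 8.4.2.2.1 counts cases only after 14 days because protection is not immediate. The last two columns subtract the same 14 days for a vaccine given as the window closes.

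| Assumed NH Day 1 | One dose: days from Day 181 to 30 June | Two doses: days from Day 209 to 30 June | One dose, less 14 | Two doses, less 14 |
|---|---|---|---|---|
| 1 Sept | 122 | 94 | 108 | 80 |
| 1 Oct | 92 | 64 | 78 | 50 |
| 1 Nov | 61 | 33 | 47 | 19 |
| 1 Dec | 31 | 3 | 17 | 0 |

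**4. Effect on VE.** Bias depends on cases, not days. Let g be the share of comparator cases that would fall after a late vaccine could act, and c the share of comparator children so vaccinated. The documents give neither. Suppose the non-study vaccine has VE 50% in comparator children and adds nothing in QIVc children. Comparator cases are then multiplied by 1 − 0.5gc, and

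observed HR = 0.50 / (1 − 0.5gc).

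Estimated VE when the true value is 50%:

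| g | c = 1% | c = 5% | c = 10% | c = 20% |
|---|---|---|---|---|
| 2% | 49.99% | 49.97% | 49.95% | 49.90% |
| 10% | 49.97% | 49.87% | 49.75% | 49.49% |
| 20% | 49.95% | 49.75% | 49.49% | 48.98% |

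For example, g = 20% and c = 5% give 0.50 / (1 − 0.005) = 0.5025, a loss of 0.25 points. Only the extreme corner, g and c both 20%, loses about 1 point. If 381 events were analysed, power would be 89.9% at VE 49.75% and 87.0% in that corner, against 90.7%.

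**5. Other safeguards.** None appears in the documents supplied. SAP 6.1 gives no window of its own for non-study influenza vaccine, and SAP 11.1 does not censor at receipt.

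**The case against.** The best reply is that 6.5 does not settle PPS membership. Exclusion is discretionary even inside the window. SAP 6.1 says its list of major deviations is not exhaustive, and sends the exclusions to a deviation specification finalised before unblinding. SAP 7.4 also allows exclusion for other reasons fixed in advance. That specification is not among the documents and could already close the gap. This stands, and it limits what can be claimed.

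Three stronger readings are tempting, and the documents support none of them.

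- *Late-vaccinated comparator children will stay in the PPS.* They are not flagged by 6.5; whether they stay depends on the specification.
- *The primary result is at risk.* The FAS keeps these children under any deviation rule, and dilution of the comparator group cannot produce a false success.
- *The uncovered share of calendar time measures the problem.* It would do so only under a constant hazard. The plan ties its interim timing to the Northern Hemisphere peak season and to April (Protocol 8.6), so days in May and June cannot be assumed to carry the same risk as winter days.

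The rule also applies to both arms. Bias toward zero assumes similar late uptake in the two arms and at least as much gain in comparator children as in children who already received QIVc, which is the natural expectation.

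None of this removes the mismatch. Section 6.5 states a definite end date, and that date conflicts with the efficacy window.

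**Conclusion.** The point holds as an inconsistency of small consequence. Where Day 181 or Day 209 precedes season end, the rule in Protocol 6.5 misses a non-study influenza vaccine given while the child is still in efficacy follow-up, and a comparator child so vaccinated may remain in the PPS repeat.

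The likely effect is well under 1 VE point, toward zero. It is at most about 0.25 points if no more than 5% of comparator children are vaccinated late and no more than 20% of comparator cases follow. These ranges, the Day 1 dates and the 50% efficacy of the non-study vaccine are assumptions. The FAS result and the 381-event target do not change.

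**What to change.** Reconcile Protocol 6.5 with Protocol 3.2 and 8.1.1.2 and SAP 2.1.2 and 11.1, so that the PPS deviation window for non-study influenza vaccine runs from Day 1 to the end of each subject's efficacy follow-up. The two SAP sections should first agree on when that follow-up ends. This concerns only how the data are classified and analysed, not which vaccines a child may receive.

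In the deviation specification, before unblinding, state that for a non-study influenza vaccine given after Day 181/209 the PPS drops only the follow-up after receipt, by censoring on that date. SAP 7.4 already allows part of a subject's data to be removed. Dropping the whole child would discard about six months of valid follow-up, including any earlier case, and could select on being event-free.

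The cost is one phrase in the protocol, one line in the specification and slightly less PPS follow-up time. No new data are needed, because vaccinations are already recorded to the later date.

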6.6 Vaccine Supply, Labeling, Storage and Tracking

The Sponsor or delegate will ensure the following:

- Supply the study vaccine(s)/saline.

- Appropriate labeling of all study vaccines provided that complies with the legal requirements of each country where the study is to be performed.

The investigator must ensure the following:

- Acknowledge receipt of the study vaccines by a designated staff member at the site, including:
 - Confirmation that the vaccines were received in good condition
 - Confirmation to the Sponsor or delegate of the temperature range during shipment from the Sponsor to the investigator's designated storage location
 - Confirmation by the Sponsor or delegate that the vaccines are authorized for use.
- Proper storage of the study vaccines, including:
 - Storage in a secure, locked, temperature-controlled location.
 - Proper storage according to the instructions specified on the labels.
 - Appropriate record keeping and inventory of the study vaccines, including regular documentation of adequate storage temperature.
- Appropriate use of the study vaccines, including:
 - Not use of vaccines prior to receipt of authorization for use from the Sponsor or delegate.
 - Use only in accordance with the approved protocol.
 - Proper handling, including confirmation that the vaccine has not expired prior to administration.
 - Appropriate blinded documentation of administration of vaccines to study subjects including:
 - Date, dosage, batch/lot numbers, expiration dates, unique identifying numbers assigned to subjects and study vaccines, and time of vaccine administration. This information will be maintained in an accountability log that will be reviewed by the site monitor.
 - Reconciliation of all vaccines received from the Sponsor or delegate. Reconciliation is defined as maintaining records of which and how many vaccines were received, which vaccines were administered to subjects, which vaccines were destroyed at the site, and which vaccines were returned to the Sponsor or delegate, as applicable.
- Proper adherence to the local institutional policy with respect to destruction of study vaccines.

- Complete record keeping of vaccine use, wastage, return or destruction, including documentation of:
 - Copy of the site's procedure for destruction of hazardous material.
 - Number of doses destroyed, date of destruction, destruction code (if available), method of destruction, and name of individual performing destruction.

Vaccines that have been stored differently from the manufacturer's indications **must not** be used unless the Sponsor (or delegate) provides written authorization for use. In the event that the use cannot be authorized, the Sponsor or delegate will make every effort to replace the vaccine supply. All vaccines used in conjunction with this protocol must be stored separately from normal hospital/practice stocks to prevent unintentional use of study vaccines outside of the clinical study setting.

Monitoring of vaccine accountability will be performed by the study monitor during site visits and at the completion of the study.

At the conclusion of the study, and as appropriate during the course of the study, the investigator must ensure that all unused study vaccines, packaging and supplementary labels are destroyed locally (upon approval from Sponsor/delegate) or returned to the Sponsor or delegate.

